that incisions are covered with a postsurgical cover dressing, for up to a period of 48 hours, to help control postoperative bleeding, absorb exudate, provide mechanical protection, help to reduce edema and provide protection from exogenous sources (Mangram *et al* 1999). Multiple patient comorbidities, environmental factors and the type and length of surgery may elevate certain groups of patients into a higher level of risk of developing a post-surgical complication: calling for a higher degree of vigilance and postsurgical intervention. Surgical complications include; wound dehiscence, infection (deep or superficial), hematomas, seromas, tissue necrosis and delayed incision healing. Complication rates can range from 19% in patients requiring open reduction and internal fixation (ORIF) of tibial plateau, pilon and calcaneus fractures (Stannard *et al* 2011) up to 50% in high energy trauma wounds (Stannard *et al* 2006). These complications can have a high degree of morbidity for the patient and further sequelae may result in additional surgical procedures or revisions, a lower functional status for the patient, an increased in length of hospital stay (LOS) and a higher cost for the healthcare provider.

Traditional NPWT has been shown to be an effective adjunct therapy in the treatment of acute and chronic wounds, but the emergence of incisional NPWT (iNPWT) and supporting evidence is growing momentum. *In vitro* studies have shown that iNPWT may help to improve the stimulation of blood flow, help manage exudate, help to reduce edema, provide a mechanical and “splinting” effect on the incision and provide mechanical protection from the environment. Its impact on the prevention or reduction of post-surgical incision complications is still in its infancy, but recent studies pioneered by Stannard *et al* (Stannard 2011) have been encouraging and have demonstrated a statistically significant reduction in infection and dehiscence in patients considered as high-risk following severe skeletal trauma.

The aim of this study is to assess the prevention of incision healing complications in patients undergoing KA and THA treated with either Single-Use Incisional NPWT compared to standard of care dressings.

PRIMARY OBJECTIVE

Compare PICO wound dressing to current MOI standard of care for postoperative incision management in Knee Arthroplasty (KA) or Total Hip Arthroplasty (THA) patients.

Outcome Measures:

- Primary: Incision appearance at 1, 2 and 5 weeks postop

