- VAS (Incision Healing Assessment Form) 0-10 continuous, based on standardized digital image (1 week) and exam (2 and 5 weeks). The VAS can be completed by the PI, any of the sub-investigators, or any properly trained physicians or RN associated with the project. If the VAS is completed based on an incisional photo, study staff will collect the exact date the photo was taken.
- If the subject will not be returning 2 weeks postoperatively as standard of care, they will be asked to take another standardized digital image at 2 weeks, and the 2 week follow-up will be done over the phone.

SECONDARY OBJECTIVES

To assess complications between patients treated with either PICO or standard care dressings. **Outcome Measures:**

- Secondary: Daily phone calls for first week; follow-up appointments
 - Drainage amount
 - User-friendliness for patient
 - Complications
 - Return to OR
 - Need for antibiotics

Data Analysis:

- Compare TOTAL PICO vs. SOC incision appearance VAS and drainage amount using t-Test
- Compare Primary JA (joint arthroplasty) PICO vs. SOC incision appearance VAS and drainage amount using t-Test
- Compare Revision JA PICO vs. SOC incision appearance VAS and drainage amount using t-Test
- Compare TOTAL PICO vs. SOC for all other outcome measures using chi-square based on number in each category
- Compare Primary JA PICO vs. SOC for all other outcome measures using chi-square based on number in each category
- Compare Revision TJA PICO vs. SOC for all other outcome measures using chi-square based on number in each category
- Post-hoc assessment of risk factors – ASA level, surgeon, BMI

EVALUATION DESIGN

The study will comprise a prospective, open labeled, single-centre study to determine the efficacy of a Single-Use Negative Pressure Wound Therapy (NPWT) System (PICO) in the prevention of postsurgical incision healing complications in patients undergoing KA and THA. The study will be comparative and randomized according to a pre-determined randomization schedule. The study will be open-labeled due to the physical appearance of both the investigational product and standard dressings, which will be impossible to blind to both the investigator and/or patient. Patients will be stratified according to the type of surgical procedure (KA/THA) and primary or revision procedure. Patients will be followed up for a period of 5 weeks, to determine if there are any latent problems with infection or dehiscence.

PICO

IRB Project # 1208434

Version 8

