24MAR2016

NUMBER OF PATIENTS

1000 patients will be enrolled into the evaluation.

INCLUSION CRITERIA

- 1 – Patient ≥ 18 years old
- 2 - Male or non-pregnant females
- 3 – Patient is scheduled to have a surgical procedure for Knee Arthroplasty (either total knee arthroplasty or unicompartmental knee) or Total Hip Arthroplasty. May be Primary or Revision Procedure.
- 4 - The patient is able to understand the trial and is willing to consent to the trial

EXCLUSION CRITERIA

- 1 – Patients who in the opinion of the investigator may not complete the study for any reason
- 2 - Patients with a known history of poor compliance with medical treatment
- 3 - Patients who have participated in this trial previously and who were withdrawn
- 4 - Patients with known allergies to product components (silicone adhesives and polyurethane films (direct contact with wound), acrylic adhesives (direct contact with skin), polyethylene fabrics and super-absorbent powders (polyacrylates) (within the dressing)
- 5 – Patients not capable of obtaining a standardized digital picture and submitting it to the site.

ASSIGNING PATIENTS TO TREATMENT

Patients who meet all the inclusion criteria will be randomized to treatment according to a pre-determined randomization schedule. Randomization method will be [1:1](#), PICO versus standard postsurgical dressings, taken from a pre-assigned randomization table. The patient will be randomized to the application of either PICO or standard postsurgical dressings. If a patient is having a bilateral procedure, they will receive the same dressing treatment on both sides.

TREATMENT REGIME

Patients will be assessed against the eligibility criteria to determine their suitability for inclusion in the study.

Pre-Trial	
Investigator discusses study with the patient and provides the patient with a Patient Consent Form
 
Patient provides written consent to participate in the study
 
Patient functionality and QoL (quality of life) assessment (SF12)

Day 0	
Patient provides written consent to participate in the study (if not done prior to day 0)
 
Complete eligibility checklist, relevant medical history and concomitant medication
 
Patient functionality and QoL (quality of life) assessment (SF12) (*if not done at Pre-Trial visit)
 
ASA level
 
BMI
 
Operative procedure (KA or THA)
 
Incision assessment following procedure
 
First dressing application

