2. Mangram, AJ, Horan TC et al., (1999). The Hospital Infection Control Practices Advisory Committee. Guideline for Prevention of Surgical Site Infection, 1999. Special Report. *Infection Control and Hospital Epidemiology*, Vol 20, No 4.

APPENDIX 1

Patient Risk Grading System

The index values range from 0 to 3 points and are defined by three independent and equally weighted variables. One point is scored for each of the following when present: (1) American Society of Anesthesiologists (ASA) Physical Status Classification of >2, (2) either contaminated or dirty infected wound classification, and (3) length of operation >T hours, where T is the approximate 75th percentile of the duration of the specific operation being performed.

Calculation.....(1) + (2) + (3) = RI

(1) Physical Status Classification, American Society of Anesthesiologists*

Code Patient's Preoperative Physical Status

- 1 Normally healthy patient
- 2 Patient with mild systemic disease
- 3 Patient with severe systemic disease that is not incapacitating
- 4 Patient with an incapacitating systemic disease that is a constant threat to life
- 5 Moribund patient who is not expected to survive for 24 hours with or without operation

APPENDIX 2

VAS Scale: PICO Study Incision Healing Assessment Form. Used to represent the assessment of incision healing based on in-person visual appearance, or appearance based on standard digital photograph.

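### Patients are stratified by knee/hip and by primary/revision, but the all-patient VAS comparison is a t-test that uses neither factor

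*Combined protocol and SAP*

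**What the plan says.** **Stratification.** Evaluation Design: "Patients will be stratified according to the type of surgical procedure (KA/THA) and primary or revision procedure". Assigning Patients to Treatment gives 1:1 allocation from a pre-assigned table and does not mention the strata again.

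**Outcome.** Primary Objective: "Primary: Incision appearance at 1, 2 and 5 weeks postop", measured as "VAS (Incision Healing Assessment Form) 0-10 continuous, based on standardized digital image (1 week) and exam (2 and 5 weeks".

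**Analysis.** The Data Analysis list under Secondary Objectives has "Compare TOTAL PICO vs. SOC incision appearance VAS and drainage amount using t-Test", then the same t-test in primary and in revision arthroplasty separately. No covariate is named for any of these. Other patient factors appear only as "Post-hoc assessment of risk factors – ASA level, surgeon, BMI".

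**Day 0.** After the operation, the Day 0 row of the Treatment Regime lists "Incision assessment following procedure" and then "First dressing application". The first item has no scale, form or assessor attached and appears in no analysis.

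**The concern.** Stratifying makes the arms alike in their mix of knee and hip, primary and revision cases. The difference in mean VAS then varies less from one randomisation to the next. A two-sample t-test does not know this. It estimates its error from the total spread of VAS within each arm, including any spread that comes only from the mix of operations. If VAS differs between strata, the reported standard error is too large, the interval too wide and the test conservative.

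What is at stake is precision in the primary comparison, given up although both factors are known for every patient before treatment.

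**Working it through.** **Inputs from the documents.** 1000 patients (Number of Patients), allocated 1:1 (Assigning Patients to Treatment), so 500 per arm. There are two stratification factors (Evaluation Design).

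**Not in the documents.** Significance level, power, target difference, SD, dropout, stratum sizes and stratum means. I assume two-sided 0.05, 80% power, no dropout and one VAS value per patient.

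**Step 1: the plan's own figure.** The 1000 cannot be reproduced because no inputs are given for it. As a reference only, the difference that 500 per arm detects with 80% power is (1.960 + 0.842) × √(2/500) = 0.177 SD.

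**Step 2: where each factor is used.**

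| Listed VAS analysis | KA/THA | Primary/revision |
|---|---|---|
| All patients, t-test | not used | not used |
| Primary only, t-test | not used | by restriction |
| Revision only, t-test | not used | by restriction |
| Post hoc: ASA level, surgeon, BMI | not used | not used |

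The separate primary and revision tests each answer a subgroup question. They are not combined into an overall estimate, so they do not repair the all-patient comparison. Both also ignore KA/THA.

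**Step 3: size of the loss.** Let R² be the share of VAS variance that lies between strata. The t-test reports variance V = 4σ²/1000. With arms balanced within strata, the true variance is V(1 − R²). Hence:

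- reported over true standard error = 1/√(1 − R²)
- actual two-sided error rate of the t-test = 2[1 − Φ(1.960/√(1 − R²))]
- power at 0.177 SD, t-test = Φ(0.842/√(1 − R²))
- power at 0.177 SD, adjusted model = Φ(2.802/√(1 − R²) − 1.960)

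| Assumed R² | Standard error ratio | Error rate of t-test | Power, t-test | Power, adjusted |
|---|---|---|---|---|
| 0 | 1.000 | 5.0% | 80.0% | 80.0% |
| 0.01 | 1.005 | 4.9% | 80.1% | 80.4% |
| 0.04 | 1.021 | 4.5% | 80.5% | 81.6% |
| 0.09 | 1.048 | 4.0% | 81.1% | 83.6% |
| 0.25 | 1.155 | 2.4% | 83.4% | 89.9% |

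If the table did not in fact balance arms within strata, the t-test's standard error would be right for its own estimate and its power would be 80.0% in every row. The adjusted column would be essentially the same.

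**Step 4: what such an R² requires.** Take one factor split evenly, the most favourable case, with stratum means d within-stratum SDs apart. Then R² = 0.25d²/(1 + 0.25d²), so d = 2√(R²/(1 − R²)). For R² of 0.01, 0.04, 0.09 and 0.25 this gives d = 0.20, 0.41, 0.63 and 1.15. An uneven split needs a larger d for the same R².

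**Step 5: the optional Day 0 covariate.** The Day 7, 14 and 35 rows each name the VAS form; the Day 0 row does not. If a Day 0 score existed and correlated r with later VAS, the error variance would fall by r². For r = 0.2, 0.3 and 0.5 that is 4%, 9% and 25%. The equivalent unadjusted sample, 1000/(1 − r²), is 1042, 1099 and 1333. If r is near zero, almost nothing is gained. The documents give no value of r.

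**The case against.** The strongest reply is that nothing here is invalid. In a 1:1 randomised trial the unadjusted difference in means is unbiased, and with stratification the t-test errs on the conservative side. Primary and revision cases are also compared separately, and surgeon is looked at post hoc. With 1000 patients and modest stratum differences, the gain is a few percent of variance. All of this stands, and it limits the point to efficiency. It does not explain why the factors chosen for stratification are left out of the all-patient comparison.

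A reader might infer something stronger: that the trial already holds a baseline VAS taken before any dressing and discards it. The documents do not support that. The Day 0 row names no scale, while the three later rows name the form. The primary outcome is defined at weeks 1, 2 and 5 only. Appendix 2 describes the form as "Used to represent the assessment of incision healing based on in-person visual appearance" or from a photograph, so it could be used on Day 0, but nothing ties it to that day. A score of healing on a just-closed incision may also vary little or predict later appearance weakly.

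Nor is a Day 0 score automatically safe as a covariate. The trial is open-label, and the documents do not say when allocation becomes known relative to closure. A score given by someone who knows the arm could differ by arm, and adjusting for it could then introduce bias. The order in the Day 0 list rules out a physical effect of the dressing, but not this.

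**Conclusion.** The point holds as a matter of precision. The all-patient VAS comparison ignores both stratification factors, and KA/THA is used nowhere in the listed analyses. If VAS differs between strata, the standard error is too large: about 0.5% at an R² of 0.01, 2% at 0.04, 5% at 0.09 and 15% at 0.25. If strata do not differ, nothing is lost. These figures assume arms balanced within strata. The power figures in the working also rest on two-sided 0.05 and no dropout. There is no bias, and the planned t-test would not give a misleading positive result on this account. This is a worthwhile improvement, not an error that threatens the trial. The Day 0 covariate is a separate and optional addition of unknown value.

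**What to change.** **Main change.** At each of weeks 1, 2 and 5, replace the all-patient t-test of VAS with a linear model with terms for treatment, KA/THA and primary/revision. Report the adjusted mean difference with its confidence interval. This costs one sentence in the analysis plan and needs no new data, because both factors are recorded in order to stratify. It can be applied to patients already enrolled.

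**Optional and secondary.** State what the Day 0 incision assessment records and whether it is descriptive only. If it is to be a covariate, record it on the same 0-10 form before allocation is known, and prespecify it in the model above. This costs more than an extra mark on a form: scoring before allocation is opened may change how theatre staff work, a rule is needed for bilateral patients with two incisions, and patients enrolled before the change may have no score. If these conditions cannot be met, leave the Day 0 item out of the model and make the main change alone.

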Days 1-7 (following surgery)	
Daily communication with the subject (in person or phone contact) to collect the following information:
 
○ Drainage amount○ User-friendliness for subject (including ease of use and subject's opinion of the noise associated with the PICO device.○ Assessment of Complications○ Assessment of return to OR○ Assessment of need for antibiotics

	
*On the days within this window that fall on a weekend or holiday, the subject will not be contacted, but rather asked for a summary of this information on the next business day. If the subject is unreachable despite the site's best effort for one or a number of the days in this window, the subject will be asked to give a summary of the "missed" days.

Day 7 (1 week postoperative, +/- 3 days)	
Incision appearance: Standard digital photo of the incision (taken by the subject, family member, friend, or caregiver). Subject will submit this photo to the site.
 
VAS (Incision Healing Assessment Form) will be completed based on photo of incision.

Day 14 (+/- 7 days)	
Incision appearance: Physician exam; VAS (Incision Healing Assessment Form); Drainage amount; Assessment of complications; Assessment of return to OR; Assessment of need for antibiotics.
 
(If the subject will not be returning 2 weeks postoperatively as standard of care, they will be asked to take another standardized digital image at 2 weeks, and the 2 week follow-up will be done over the phone.)

Day 35 (+/-14 days)	
Incision appearance: Physician exam; VAS (Incision Healing Assessment Form); Drainage amount; Assessment of complications; Assessment of return to OR; Assessment of need for antibiotics.
 
Functionality and Patient's QoL Assessment (SF12)

Study Completion	Reason for Study Completion

ADVERSE EVENTS

All adverse events reported spontaneously by the patient or in response to questioning or observation by the Investigator will be recorded.

ETHICS/IRB APPROVAL

Before the start of the trial the Investigator will submit the trial to the local independent Ethics Committee/Institutional Review Board (IRB) for review and approval.

PATIENT CONSENT

Before being recruited to the clinical trial, the patient must have given written informed consent to participate.

REFERENCES

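### Drainage is collected on nine scheduled occasions, with at least two first-week days reported by later summary, but the plan does not say which value enters its t-test and does not use the randomisation strata

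*Combined protocol and SAP*

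**What the plan says.** Secondary Objectives gives the source of the drainage data as "Secondary: Daily phone calls for first week; follow-up appointments". The Treatment Regime table, row Days 1-7, asks for "Daily communication with the subject (in person or phone contact) to collect the following information", with drainage first on the list. The rows for day 14 and day 35 list drainage again.

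The note to the Days 1-7 row limits this. On weekend days and holidays "the subject will not be contacted, but rather asked for a summary of this information on the next business day". Days on which the patient could not be reached are also covered by a summary. The table does not say whether a summary is a total, an average, the worst day or a day-by-day recall, and it gives no unit for drainage.

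Data Analysis has three lines on drainage. The first is "Compare TOTAL PICO vs. SOC incision appearance VAS and drainage amount using t-Test". The other two repeat that test within primary procedures and within revision procedures. None names a day, a visit or a way of combining values. Evaluation Design stratifies patients by procedure type (KA or THA) and by primary or revision surgery. The comparison in all patients uses neither factor.

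**The concern.** A two-sample t-test takes one value per patient, and this schedule yields several. Someone must decide whether to use one day, a week's total or mean, the follow-up visits, or each occasion in turn. As written, that decision can be made after the data are seen, in an open-label study, for the first-listed secondary outcome.

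The weekend rule adds to the problem. The post-operative days that lack a same-day report depend on the weekday of surgery. Any analysis by day would therefore mix same-day reports with later summaries, in a proportion that changes from day to day.

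Leaving the strata out of the comparison in all patients also gives up precision wherever procedure type or revision status predicts drainage. The documents give no figures from which to size that loss.

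**Working it through.** **Inputs from the documents.** Number of Patients: "1000 patients will be enrolled into the evaluation". Assigning Patients to Treatment: 1:1, "PICO versus standard postsurgical dressings, taken from a pre-assigned randomization table", hence about 500 per arm. Drainage occasions: 7 + 2 = 9.

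**Inputs assumed, because the documents give none.** Two-sided alpha 0.05; equal correlation r between occasions, 0.2 to 0.8; surgery spread evenly over Monday to Friday; no dropout.

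**1. The plan's own figure.** The sample size of 1000 cannot be reproduced, because no alpha, power, effect or SD is given. By inversion only, 500 per arm has 80% power for (1.960 + 0.842) × √(2/500) = 0.177 SD. This is used below as a benchmark and says nothing against the sample size.

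**2. Calendar.** Any seven consecutive days contain one Saturday and one Sunday. The days without contact are:

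| Surgery on | Post-operative days without contact |
|---|---|
| Monday | 5, 6 |
| Tuesday | 4, 5 |
| Wednesday | 3, 4 |
| Thursday | 2, 3 |
| Friday | 1, 2 |

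With even Monday-Friday surgery, the share of patients without a same-day value on days 1 to 7 is 20, 40, 40, 40, 40, 20 and 0%. These sum to 200%, that is, two days per patient. Holidays and missed calls add to this.

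**3. Multiplicity, if each occasion were tested.** With nine independent tests, 1 − 0.95^9 = 37%. With equal correlation, simulation gives about 33%, 27% and 20% at r = 0.3, 0.5 and 0.7. This is for all patients only; the primary and revision lines would add further tests.

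**4. Does a seven-day mean gain power over one day?** With equal SD on each day, Var(mean)/Var(one day) = (1 + 6r)/7, which is 0.40, 0.57 and 0.74 at r = 0.3, 0.5 and 0.7. If the mean difference is the same on all seven days, a single-day test with 50% power becomes Φ(1.96/√ratio − 1.96) = 87%, 74% and 62%. That result depends on the sustained effect. Against a day-1 test with 80% power (0.177 SD, 500 per arm), the seven-day mean has:

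| Effect over the week | r = 0.2 | r = 0.5 | r = 0.8 |
|---|---|---|---|
| Constant, SD constant | 99.9% | 96.0% | 86.8% |
| Linear decline, SD declining with it | 99.8% | 95.4% | 86.5% |
| Linear decline, SD constant | 81.5% | 56.3% | 42.0% |
| Days 1-3 only, SD constant | 57.2% | 35.5% | 26.1% |
| Days 1-2 only, SD constant | 29.7% | 18.4% | 14.0% |

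With constant SD, break-even is an average effect of √((1 + 6r)/7) = 56%, 76% and 91% of the day-1 effect at r = 0.2, 0.5 and 0.8.

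**5. Why the summary must be defined.** Suppose drainage falls linearly as 7/7, 6/7, …, 1/7. The true mean is 4/7 = 0.571.

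- Two-day total entered as one of six reports: 4/6 = 0.667.
- Two-day average entered as one unweighted report: Monday surgery (23/7 + 2.5/7)/6 = 0.607; Friday surgery (15/7 + 6.5/7)/6 = 0.512.
- Contacted days only: Monday (23/7)/5 = 0.657; Friday (15/7)/5 = 0.429.
- Two-day average weighted by its two days: Monday (23/7 + 2 × 2.5/7)/7 = 0.571; Friday (15/7 + 2 × 6.5/7)/7 = 0.571.

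Only the day-weighted mean (or the total) recovers the same value whatever the weekday of surgery.

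**The case against.** The strongest reply is that the plan lists no daily or per-contact test. It names the calls and appointments as sources of data and then speaks of a drainage amount, which fits one total per patient just as well. A reader might infer nine separate t-tests, but the documents do not say so. This stands: the 20-33% error rate is conditional on that reading, and so is the mixing of same-day and summarised values in day-by-day tests.

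A reader might also infer that a first-week mean is more powerful in general. The documents give no effect, SD, correlation or time course for drainage, and step 4 shows the comparison going either way. No general claim of power can be made.

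A third inference is that the weekend rule biases the comparison. The rule is the same in both arms, and randomisation should balance the weekday of surgery. Recall could differ by arm in an open-label study, but nothing in the documents shows that it does, and averaging would not remove it.

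It is also fair to say that averaging alone does not settle the weekend problem, and that a repeated-measures model would serve too. The first is met by defining the summary and its weight. The second is a reasonable alternative, but it would still need the same definition. What the reply leaves untouched is that the value to be tested is undefined and the strata are unused.

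**Conclusion.** The point holds as a modest improvement to a secondary analysis. The documents establish that drainage is collected on nine scheduled occasions, that at least two first-week days per patient are reported later as a summary, that the t-test has no rule for combining values, and that the comparison in all patients ignores the stratification factors.

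The expected consequence is added noise and an endpoint that could be chosen after the data are seen. The 20-40% of patients without a same-day value on each of days 1-6 rests on even Monday-Friday surgery. The case for one first-week value rests on fixing the endpoint in advance and avoiding multiple tests. Power is a further gain only if the effect lasts through the week or if effect and SD decline together; it can be a loss if the effect is confined to the first days.

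**What to change.** In Data Analysis, define drainage as one first-week value per patient: a total, or a mean that weights each report by the days it covers, with weekend and missed-day summaries included. Compare the arms once in all patients with a linear model containing KA/THA and primary/revision, in place of the unadjusted t-test. Report day 14 and day 35 drainage descriptively.

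In the Days 1-7 row of the Treatment Regime table, state the unit for drainage, and state that a summary records the amount over the days missed and how many days it covers.

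The cost is a few sentences of analysis wording and one line in the data-collection instruction, with no new visits or patients. What is given up is a confirmatory day-by-day comparison.
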